5 STUDY DESIGN

5.1 Study description

This is a Phase 2A, multicenter, single-arm, OLE study to evaluate the safety, tolerability, and efficacy of rozanolixizumab during long-term treatment of study participants with CIDP from a previous study with rozanolixizumab.

Access to CIDP04 for study participants coming from CIDP01: Study participants from CIDP01 who have completed the Treatment Period (ie, all visits up to Visit 17) without a relapse of CIDP will be offered the opportunity to be directly enrolled into this OLE study. Study participants will enter CIDP04 on the same day as the last study visit in CIDP01: Visit 17. Study participants from CIDP01 who have experienced a relapse of CIDP (during either the Treatment Period or the Observation Period), have been successfully rescued and stabilized with SOC medication and have consented to enter this OLE study, may be assessed for eligibility. The study participants who relapsed during the Treatment Period of CIDP01 will be offered entry into CIDP04 only once CIDP01 study results are available, after the blind has been broken at the end of the study, and it is confirmed they received placebo in CIDP01.

In case the study participants have a gap period between the end of the parent study and the start of this OLE study (ie, last visit in the parent study does not take place on the same day as entry of study CIDP04), a Screening Period of 2 to 5 weeks will be applicable to confirm that the study participant still meets the eligibility criteria for entry in the OLE study and allow for a smooth transition between the treatment used by the study participants during the gap period and the initiation of rozanolixizumab. The CIDP04 study includes a first 24-week Treatment Period (Part 1) followed by a second Treatment Period (Part 2) of up to 52 weeks (or until an Access Program or equivalent is in place, whichever comes first). Entry to the Treatment Period (Part 2) will be contingent to a favorable individual benefit-risk after careful individual assessment has been performed for each study participant completing Treatment Period (Part 1). An 8-week Observation Period will be followed in case of premature termination or after completion of the Treatment Periods (either at end of Part 1 for study participants not continuing in Part 2 or at end

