5 STUDY POPULATION CHARACTERISTICS

5.1 Study participant disposition

The number of participants who were enrolled, dosed, participants included in each analysis set, and participants who completed or prematurely discontinued the study, as well as the reason for discontinuation, and discontinuation due to AEs (categorised as fatal, non-fatal, other) will be presented by treatment group and overall. Screen failure reasons will be summarized, based on the ES.

In addition, the following listings will be presented by treatment group:

- Participant disposition (ES)
- Study discontinuation (ES)
- Visit dates (SS)
- Participant analysis sets (ES)

Study participant disposition will be listed based on the ES by treatment group, and will include the date of informed consent, date and time of first and last dose of IMP, date of premature termination and primary reason, and date of final contact (if applicable).

The first dose of IMP will be the first IMP infusion in CIDP01 for study participants treated with rozanolixizumab in CIDP01 or the first dose of rozanolixizumab in CIDP04 for the study participants under placebo in CIDP01.

The listing of study discontinuation will include the reason for discontinuation, period of discontinuation, with dose and number of days on that dose and the total number of days on study medication.

The number of days on IMP will be calculated as follows:

Number of days on IMP=(Date of Last Dose Received)-(Date of First Dose Received)+1

Time to discontinuation of study participation will be listed and plotted in a Kaplan-Meier-Curve for all discontinuations versus discontinuation due to COVID-19. The plot will be based on the randomized set.

Reasons for screening failures, disposition and discontinuation reasons will also be summarized based on the respective event's date relative to the COVID-19 period.

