10.2 Adverse events

Adverse events will be recorded from the time of informed consent until study completion. All AEs will be coded ([Section 3.8](#)) and categorized by relationship to rozanolixizumab.

In addition, AEs will be classified according to the Common Terminology Criteria for Adverse Events (CTCAE) Version 5.0 for severity. For any AEs where it is not possible to provide a CTCAE grading, the events will be assessed using a standard intensity classification (mild, moderate and severe).

A TEAE is defined as any event that was not present prior the first administration of IMP in CIDP04 study or any unresolved event already present before the first administration of IMP in CIDP04 study that worsens in intensity following exposure to treatment until 8 weeks following

the last administration of IMP in CIDP04 study. Adverse events starting before the first administration of IMP in CIDP04 study or later than 8 weeks after the administration of the last IMP will not be considered TEAEs. Such events will be listed only.

Where dates are missing or partially missing, AEs will be assumed to be treatment-emergent unless evidence exists that does not allow the AE to be treatment-emergent. Handling of missing dates/times for classification of AEs as TEAEs is described in [Section 4.2.7](#).

The following rules will be used to assign a TEAE to the study periods:

- **Treatment Period:** a TEAE will be assigned to the Treatment Period for the tabulations if the start date/time of the event is at the time of or after the first administration of IMP in CIDP04 study on Week 1, up to Visit 26/PEOT (non-inclusively).
- **Observation Period:** a TEAE will be assigned to the Observation Period for the tabulations if the start date/time of the event is at or after Visit 26/PEOT till 8 weeks after administration of the last IMP in CIDP04 study.
 - The Observation Period's TEAEs will be stratified by TEAEs of study participants who received/did not receive standard of care treatment (i.e. Ig treatment) between start of the Observation Period and occurrence of the TEAE.

The number and percentage of study participants who experience TEAEs will be summarized by Treatment Period, Observation Period (standard of care treatment status identified by WHODD J06BA01 and J06BA02) and Overall, with respective treatment group. The following summaries will be presented:

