- Incidence of TEAEs (overview including number and percentage of study participants with any TEAEs, serious TEAEs, discontinuations due to TEAEs, related TEAEs, TEAEs with CTCAE Grade 3 and above [or rated as 'severe' for events with no CTCAE classification], and deaths; event counts will also be included)
- Incidence of TEAEs by SOC, HLT and PT
- Incidence of TEAEs during the Dosing Period by SOC, HLT and PT
- Incidence of serious TEAEs by SOC, HLT and PT
- Incidence of non-serious TEAEs by SOC, HLT and PT
- Incidence of AEs of special interest by SOC, HLT and PT
- Incidence of AEs of interest by SOC, HLT and PT
- Incidence of TEAEs by relationship, SOC, HLT and PT
- Incidence of TEAEs by maximum relationship, SOC, HLT and PT
- Incidence of serious TEAEs by relationship, SOC, HLT and PT
- Incidence of non-serious TEAEs by relationship, SOC, HLT and PT
- Incidence of fatal TEAEs by relationship, SOC, HLT and PT
- Incidence of TEAEs by maximum intensity (mild, moderate and severe), SOC, HLT and PT

- Incidence of non-serious TEAEs above threshold of 5% of participants by SOC and PT
- Incidence of non-serious TEAEs above threshold of 5% of participants by relationship, SOC and PT
- Discontinuation due to AEs

Summary tables will contain counts of study participants, percentages of study participants in parentheses and the number of events. A study participant who has multiple events in the same SOC, HLT and PT will be counted only once in the study participant counts but all events will be included.

Adverse event summaries will be ordered by alphabetical SOC, alphabetical HLT within SOC and decreasing frequency in the treatment group.

In summaries including intensity, the CTCAE categories will be summarized according to the following categories:

- Grade 1: Mild
- Grade 2: Moderate
- Grade 3: Severe
- Grade 4: Severe
- Grade 5: Severe
- not gradable

In the case both category types are captured and the mapping to a standard intensity classification per above rule results in a class different from the standard intensity classification given in the eCRF, the worst case will be used.

These will be tabulated together with the AEs that were not classified according to CTCAE criteria i.e., all Grade 1 AEs as per CTCAE criteria will be included in the 'mild' category together with those AEs classified as mild as per the 'standard' intensity classification.

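### TEAE tables pool one dose to 76 weeks of CIDP04 treatment without person-time, so crude incidence is neither a fair group comparison nor a long-term rate

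*SAP*

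**What the plan says.** Long-term safety and tolerability is the primary objective, and occurrence of TEAEs is the primary safety variable (Protocol 3.1 and 4.1.1; SAP 2.1.1 and 2.2.1.1).

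- **Measure.** SAP 10.2: "The number and percentage of study participants who experience TEAEs will be summarized by Treatment Period, Observation Period" and overall, for each treatment group. The tables include "Incidence of TEAEs by SOC, HLT and PT". The content is set as follows: "Summary tables will contain counts of study participants, percentages of study participants in parentheses and the number of events". No denominator in time is given.
- **Window.** "A TEAE is defined as any event that was not present prior the first administration of IMP in CIDP04 study", with a further clause for worsening of earlier events. Events starting "later than 8 weeks after the administration of the last IMP will not be considered TEAEs". Within that window, the Treatment Period ends just before Visit 26/PEOT, which falls at Week 25, at Week 77 or earlier. There is no cut at Week 24.
- **Length of treatment.** The Safety Set needs one CIDP04 dose (SAP 3.5.2). Part 1 lasts 24 weeks and Part 2 up to 52. Relapse or rescue ends IMP (Protocol 6.4). "Entry to the Treatment Period (Part 2) will be contingent to a favorable individual benefit-risk after careful individual assessment" (Protocol 5.1). An Access Program can shorten Part 2 (Protocol 5.1.1).
- **Exposure.** SAP 10.1 defines only the percentage deviation from the dose, in three categories. The one duration with a formula is in SAP 5.1: "Number of days on IMP=(Date of Last Dose Received)-(Date of First Dose Received)+1". It feeds the listing of discontinuations. Its first dose is the CIDP01 infusion for participants who had rozanolixizumab there, and the first CIDP04 dose for former placebo participants.

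**The concern.** A percentage of participants with an event rises with the time they are watched. Here that time varies many-fold between participants, and it is not random: those who relapse leave treatment early, and those judged to have a favourable benefit-risk stay on. The two displayed groups are also selected differently. A participant who relapsed during CIDP01 treatment may enter only if the treatment was placebo (Protocol 5.1 and 6.1), so all such entrants fall in the newly treated column. Different relapse rates, and hence different durations, are plausible, although the documents give no figures for either.

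The column with more Part 2 time would then show more TEAEs at the same underlying rate. Conversely, a column shortened by relapse could look safer than it is. Event counts do not solve this, because without person-time they are not rates.

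The SAP already handles efficacy differently: relapse outputs are produced for Part 1 and for the whole Treatment Period (SAP 8.1.2). TEAEs get no such split. The interim analysis after Part 1 (Protocol 14.7), which could have supplied one, is cancelled in the SAP's section on interim analysis. SAP 10.2 also names a TEAE table for a Dosing Period but does not define that period.

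**Working it through.** **1. The plan's own figure.** Maximum study duration: 5 (screening) + 24 + 52 + 8 = 89 weeks, as stated in SAP 3.2.1.2. Maximum treatment is 24 + 52 = 76 weekly doses.

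**2. Time per participant.** With k weekly doses, days from first to last CIDP04 dose = 7(k − 1) + 1. The full TEAE window adds 56 days.

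| CIDP04 doses | First to last dose (days) | TEAE window (days) |
|---|---|---|
| 1 | 1 | 57 |
| 12 | 78 | 134 |
| 24 | 162 | 218 |
| 76 | 526 | 582 |

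**3. Crude incidence at a constant rate.** With r first events per participant-year (assumption), p = 1 − exp(−r × window/365.25). At r = 1, p is 14.4% after one dose, 30.7% after 12, 44.9% after 24 and 79.7% after 76. The rate is the same throughout; only duration differs.

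**4. Two groups with the same rate.** Assume 80% of group A and 50% of group B receive 76 doses and the rest 12. Each group's incidence is the weighted mean of p(76) and p(12), and the gap is (0.8 − 0.5) × [p(76) − p(12)]. Gaps are computed before rounding.

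| r per year | p(12) | p(76) | Group A | Group B | Gap (points) |
|---|---|---|---|---|---|
| 0.25 | 8.8% | 32.9% | 28.0% | 20.8% | 7.2 |
| 0.5 | 16.8% | 54.9% | 47.3% | 35.8% | 11.4 |
| 1 | 30.7% | 79.7% | 69.9% | 55.2% | 14.7 |
| 2 | 52.0% | 95.9% | 87.1% | 73.9% | 13.2 |
| 4 | 76.9% | 99.8% | 95.3% | 88.4% | 6.9 |

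A 90% against 30% mix gives 22.9, 29.4 and 26.3 points at r = 0.5, 1 and 2. With equal mixes the gap is zero at every rate. It also shrinks when events are rare or nearly universal.

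**5. Does a first-event rate remove the artefact?** With person-time censored at the first event, expected time at risk over a window c is (1 − exp(−rc))/r. Expected first events divided by that time equals r for any c, so both groups show the same rate. This relies on a constant rate. If events cluster early, a pooled rate still depends on the mix of durations, which is why a Weeks 1–24 table is needed as well.

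**6. Which denominator fits?** TEAEs count during temporary halts and for 8 weeks after the last dose. Over first-to-last-dose time, the overall rate would be inflated by 218/162 = 1.35 after 24 doses, 582/526 = 1.11 after 76, and 57-fold after one dose. Access Program entrants have only Visit 26 after treatment (Protocol 5.1), so their time at risk must end at last contact.

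**7. Days on IMP in SAP 5.1.** A previously treated direct entrant carries about 11 weeks (77 days, assumed from the length of the CIDP01 Treatment Period). That gives 162 + 77 = 239 days after 24 CIDP04 doses and 526 + 77 = 603 after 76. A previously treated gap entrant could carry 11 + 24 + 13 + 5 = 53 weeks (371 days, assumed upper end: CIDP01 treatment, longest observation, 3 months' stabilisation, longest screening). That gives 533 and 897 days. For the newly treated, the count starts at the first CIDP04 dose.

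**The case against.** The study is single-arm and descriptive. SAP 4.6 marks multiplicity as not applicable, and no between-group test of TEAEs is planned. Protocol 14.3.1 prespecifies incidence and frequencies, and the SAP delivers them. Treatment and Observation Periods are separated. Every infusion date is listed (SAP 7), as are each adverse event's onset and its days since first and most recent dose (SAP 10.2). Time to discontinuation is plotted (SAP 5.1). CIDP04 person-time can be derived from these records, so what is missing is a summary, not information. Nothing in the documents predicts that Part 2 uptake will differ between the groups, and with equal durations there is no artefact. All of this stands, and it limits the point to interpretation of the summary tables.

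Three stronger readings are tempting but unsupported.

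- A reader might infer that TEAEs are reported only as percentages. SAP 10.2 also tabulates event counts.
- A reader might infer that the figures cannot be interpreted at all. A crude percentage is a valid proportion of those dosed.
- A reader might infer that days on IMP corrupts the TEAE results. The SAP never uses it as a TEAE denominator, and the same listing shows days on the dose concerned. CIDP01 time enters only for previously treated participants. The off-drug gap before CIDP04 affects only those of them who did not enter directly.

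What remains is that the groups stand side by side in every TEAE table of a study about long-term safety, with no summary of how long each was treated or observed.

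**Conclusion.** The point holds in a limited form. Without CIDP04 person-time, crude TEAE incidence cannot be fairly compared between the newly and previously treated columns if their durations differ, and it cannot be read as a long-term rate.

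The artefact is about 11 to 15 points at 0.5 to 2 first events per participant-year under the 80% against 50% mix, and about 7 points at 0.25 or 4 per year. Its true size is unknown. Event rates, the share of each group receiving long treatment and the 12-dose early stop are all assumptions, the rate is taken as constant, and the number of participants is redacted. It could be zero.

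This is a worthwhile, cheap improvement to the primary safety reporting. It does not invalidate the planned tables.

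**What to change.** 1. **SAP 10.1.** Summarise, by group and overall, CIDP04 treatment duration (first to last CIDP04 dose) and CIDP04 time at risk. Time at risk runs from the first CIDP04 dose to the earlier of last CIDP04 dose + 8 weeks or last contact. Temporary halts stay in, so that it matches the TEAE definition.
2. **SAP 10.2.** Next to the crude percentages, add events per 100 participant-years at risk, and first-event rates with person-time censored at the first event. Use the time at risk of the period tabulated.
3. **SAP 10.2.** Add TEAE tables for Part 1 (Weeks 1–24) and for Part 2 among those who entered it, alongside the overall table. Label the Part 2 table as a selected group.
4. **SAP 5.1 (secondary).** In the discontinuation listing, show CIDP01 and CIDP04 days on IMP separately for previously treated participants.

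The cost is a few more columns and tables and some derivation programming. Dosing dates, adverse event dates and final contact dates are already listed, so no new data are needed.

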9.1.2.1 Description of adverse events

When recording an AE, the investigator should use the overall diagnosis or syndrome using standard medical terminology, rather than recording individual symptoms or signs. The eCRF and source documents should be consistent. Any discrepancies between the study participant's own words on his/her own records (eg, e-diary card) and the corresponding medical terminology should be clarified in the source documentation.

Details for completion of the Adverse Event eCRF (including judgment of relationship to IMP) are described in the eCRF Completion Guidelines.

- Mild: An event that is easily tolerated by the participant, causing minimal discomfort and not interfering with everyday activities
- Moderate: An event that causes sufficient discomfort and interferes with normal everyday activities
- Severe: An event that prevents normal everyday activities. An AE that is assessed as severe should not be confused with an SAE. Severe is a category utilized for rating the intensity of an event; and both AEs and SAEs can be assessed as severe.
- An event is defined as ‘serious’ when it meets at least 1 of the predefined outcomes as described in the definition of an SAE, NOT when it is rated as severe (eg, a severe AE may be either serious or not serious, depending on whether these criteria are also met).

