9.1.10 Management of headache

Based on current available clinical data, headache is the most commonly reported adverse drug reaction in study participants treated with rozanolixizumab. Study participants should be well informed of this potential adverse drug reaction and should be instructed on how to manage it.

Treatment of headaches should be as per national guidelines and take medical history of previous headaches, concomitant medication, and co-morbidities (eg, asthma) in consideration. In case of continued tolerance issues, and if symptomatic headache medication (eg, acetylsalicylic acid

1000mg) is not sufficient, a further step can be to reduce dose of IMP to █ (see Section 7.2).

Determination of the severity of headache will be consistent with National Cancer Institute CTCAE version 5.0. Severe headache is defined as severe pain limiting self-care activities of daily living (ADL). Self-care ADL refer to bathing, dressing and undressing, feeding self, using the toilet, taking medications. Treatment of headache will be provided as clinically indicated according to the national guidelines.

Study participants experiencing severe and/or serious headache will complete the Headache Questionnaire daily until resolution (ie, if headache becomes nonserious, moderate or mild, or completely resolved, whichever comes first). At the clinic visit when the severe headache is reported, the Headache Questionnaire will be followed by a neurological assessment (including fundoscopy). If the severe or serious headache is initially reported at a home visit or during a telephone call, the study participant should be reviewed at the study site as soon as is practically possible for further investigations. Study participants should be monitored for signs and symptoms suggestive of central nervous system involvement and evaluated immediately if other causes (eg, meningitis, intracranial bleeding) are suspected. Further neurological workup may be performed (if indicated) at the discretion of the investigator and may include a computed tomography scan, magnetic resonance imaging and/or a lumbar puncture for cerebral spinal fluid collection. In addition, samples for exploratory safety biomarkers should be collected for study participants experiencing severe or serious headache when possible (Table 5-2). These investigations will be performed to further understand the mechanism of headache in these study participants.

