14.3 Planned safety analyses

14.3.1 Safety analyses

The incidence of study participants with TEAEs will be determined. Furthermore, the absolute and relative frequencies for study participants with a given TEAE with respect to the preferred term according to the latest available version of the Medical Dictionary for Regulatory Activities

(MedDRA®), will be determined within each system organ class. Additional tables will summarize TEAEs by maximum severity and causal relationship with rozanolixizumab, as judged by the investigator. Adverse events will be categorized by severity according to the National Institutes for Health CTCAE version 5.0 grading (National Institutes for Health, 2017). In case the CTCAE grading is not available, the intensity (mild/moderate/severe) will be utilized. The TEAEs leading to discontinuation of IMP and the serious TEAEs will also be summarized. The action taken, time of onset relative to dosing, actual dose received, and duration of each AE will be listed only.

For the continuous laboratory variables, the values and changes from Baseline will be descriptively summarized at each time point. For categorized values according to the reference range, shift tables from Baseline to each post-Baseline time point will be presented for selected variables to be defined in the SAP. Values outside the reference range will be flagged in the data listings.

Descriptive statistics will be presented for ECG value and changes from Baseline over time based on the mean of the triplicate assessments at each time point. Categorical analyses for QTc, eg, QTc increase >60msec, will also be performed.

Descriptive statistics will be reported for all vital sign measurements (including BP, PR, temperature, and body weight). Measured values and changes from Baseline will be summarized by time point.

Physical and neurological examination findings and the results of any pregnancy testing will be presented in listings only. Results will be listed for any study participants who complete a headache questionnaire, undergo stool sampling, or lumbar puncture, etc.

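### SAP 10.2 classifies severity by two different rules, so an event with CTCAE Grade 1 or 2 and eCRF intensity severe can be missing from the overview row yet counted as severe in the maximum-intensity tables

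*SAP*

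**What the plan says.** **CTCAE grade first.** Protocol 14.3.1 states: "Adverse events will be categorized by severity according to the National Institutes for Health CTCAE version 5.0 grading". It then gives the fallback: "In case the CTCAE grading is not available, the intensity (mild/moderate/severe) will be utilized". The opening of SAP 10.2 agrees: "For any AEs where it is not possible to provide a CTCAE grading, the events will be assessed using a standard intensity classification". The overview table in the same section follows this order, with a row for "TEAEs with CTCAE Grade 3 and above [or rated as 'severe' for events with no CTCAE classification".

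**Worst case.** Later in SAP 10.2 a second rule appears, introduced by "In summaries including intensity, the CTCAE categories will be summarized according to the following categories". Grade 1 maps to mild, Grade 2 to moderate, and Grades 3 to 5 to severe. If both types of classification are captured and this mapping "results in a class different from the standard intensity classification given in the eCRF, the worst case will be used". The tables by intensity are TEAEs by maximum intensity and, for each AE of focus, the table by maximum intensity.

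**Recording.** Protocol 9.1.2.1 defines mild, moderate and severe for AEs generally ("Severe: An event that prevents normal everyday activities") and does not restrict the scale to ungraded events.

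**Declared changes.** SAP section 1 says that departures from the protocol analysis are documented in SAP 3.9. That section does not mention the worst-case rule.

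**The concern.** The report would present severity under two definitions without saying so. The overview row is where a reader first looks for the number of participants with high-grade events. The maximum-intensity tables are where that number is broken down by system organ class and preferred term. If both scales are recorded and differ, the breakdown can contain severe events that the overview does not count, and nothing in the planned outputs explains the gap. The intensity tables would also depart from the order that the protocol sets, without a declaration.

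This is a single-arm study whose primary objective is long-term safety and tolerability, with no formal test on these counts. What is at stake is therefore the consistency and traceability of a planned safety summary, not a decision rule.

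**Working it through.** The documents give no figure to reproduce. The check applies each rule literally to every possible record.

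**Inputs**
- CTCAE grade: none or 1 to 5, so 6 states.
- eCRF intensity: none, mild, moderate or severe, so 4 states.
- Combinations: 6 × 4 = 24. Dropping the one with neither recorded leaves 23, of which 5 × 3 = 15 have both, 5 have a grade only and 3 have an intensity only.

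**Rules**
- Overview (SAP 10.2 overview row, same order as Protocol 14.3.1): counted if grade ≥ 3; if there is no grade, counted if intensity is severe.
- Intensity tables (SAP 10.2 mapping and worst-case sentence): class = the worse of the mapped grade and the eCRF intensity.

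**Only one scale recorded (8 combinations).** Both rules use whatever is recorded and always agree.

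**Both scales recorded (15 combinations)**

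| CTCAE grade | eCRF intensity | In overview row? | Severe in intensity tables? |
|---|---|---|---|
| 1 | mild or moderate | no | no |
| 1 | severe | **no** | **yes** |
| 2 | mild or moderate | no | no |
| 2 | severe | **no** | **yes** |
| 3, 4 or 5 | mild, moderate or severe | yes | yes |

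The rules disagree on 2 of the 23 combinations (2 of the 15 with both scales), always in the same direction. For the same set of events, the overview count can only be equal to or lower than the severe count under the intensity rule. A participant's classification differs only if the discordant event is not accompanied, in the same table cell, by another event of Grade 3 or higher (or by an ungraded severe event).

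**After harmonising.** With either rule used in both places, the disagreements fall from 2 of 23 to 0 of 23.

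**The case against.** The best case for leaving the text alone has four parts.

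1. **Dual recording is a contingency.** The opening of SAP 10.2 reserves the intensity scale for events that cannot be graded, so there may be few or no records with both. This is fair. How often both are filled in depends on the eCRF and its completion guidelines, which are not in the documents. But the SAP writes a rule for this case, and Protocol 9.1.2.1 does not confine the intensity scale to ungraded events. The case has to be handled consistently.

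2. **The tables carry different labels.** The overview row is labelled by CTCAE grade and the others by intensity, so they could be read as different quantities. The bracketed fallback weakens this, because it puts ungraded severe events in the same row and so makes it the severe category. Nor can the overview be treated as one more summary including intensity to which the worst case applies: its own wording limits the use of intensity to events without a grade.

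3. **Worst case is conservative.** That is a defensible choice for a safety study. The defect is that it is used in some tables only, against Protocol 14.3.1 and without declaration.

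4. **The AE listing shows severity/intensity.** It does, but it is not specified to flag discordant events, so it would not by itself reconcile the counts.

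A reader might also infer that discordance is bound to arise for headache, because the general definition of severe intensity in Protocol 9.1.2.1 differs from the self-care anchor in 9.1.10 ("Severe headache is defined as severe pain limiting self-care activities of daily living (ADL"). The documents do not support that. Section 9.1.10 directs that headache severity be determined consistently with CTCAE version 5.0, and 9.1.11 does the same for diarrhea. Different anchors make discordance possible; they do not show that it will occur.

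**Conclusion.** The inconsistency is real and is in the text. An event with CTCAE Grade 1 or 2 and eCRF intensity severe can be absent from the overview row and severe in the maximum-intensity and AEs-of-focus tables. It requires both scales to be recorded and to disagree in that one direction. The worst-case rule departs from Protocol 14.3.1 and is not declared in SAP 3.9.

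Three stronger readings are tempting and should not be drawn.

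- **That the primary variable is compromised.** It is the occurrence of TEAEs, and a severity rule does not change whether an event occurred. Severe TEAEs are not among the listed safety variables either.
- **That the number of affected participants can be projected.** The documents give no discordance rate and no number of TEAEs per participant, and the sample size is redacted. Any projection would rest wholly on assumed values and on independence between events. The effect could be zero.
- **That CTCAE-first is the only acceptable rule.** It is the default because it matches the protocol; the worst case applied throughout and declared would also remove the conflict.

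The conclusion rests on reading both SAP rules literally. The size is 2 of 23 possible record types, with the frequency in practice unknown.

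**What to change.** Use one severity derivation in every table in SAP 10.2.

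**Default, consistent with Protocol 14.3.1.** Replace the worst-case sentence with a rule to this effect: where a CTCAE grade is recorded, it determines the class in all summaries (Grade 1 mild, Grade 2 moderate, Grade 3 or higher severe); the eCRF intensity is used only for events with no grade. Add a flag in the AE listing for events where both are recorded and the classes differ.

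**Alternative.** If the sponsor prefers the worst case, apply it to the overview row as well, reword that row accordingly, and list the rule in SAP 3.9 as a change from Protocol 14.3.1.

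**Cost.** The default needs one SAP sentence, one derivation and one listing flag; no new data are collected. Its downside is that severe counts in the intensity tables may be lower than under the present text, because an event that the investigator rated severe but graded 1 or 2 would be shown by its grade. The flag keeps those events visible.
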